### 3.2 NUMBER OF SUBJECTS

Up to 20 subjects from the main Study ZX008-1503 will have the option to participate in sub-study ZX008-1503-SS01 upon separate consent and fulfillment of entry criteria as detailed in Sections 4.1 and 4.2. Subjects will be approached sequentially until the target number of participants is reached.

### 3.3 STUDY DURATION

The duration of the main Study ZX008-1503 for an individual who enters from Study ZX008-1501 or ZX008-1504 Cohort 2 is up to approximately 54 weeks. All subjects will receive ZX008 for up to approximately 52 weeks in Study ZX008-1503 and all subjects, including those who prematurely discontinue from the study, will undergo an up to 2-week taper of study medication, at the conclusion of the study. Subjects will be permitted to participate in the sub-study for the initial 12 weeks of participation in the main OLE study (ZX008-1503). Subjects may have the opportunity to extend participation in the sub-study for up to 24 weeks.

### 3.4 NUMBER OF STUDY CENTERS

It is anticipated that sub-study subjects will be enrolled from approximately 5 to 10 study sites participating in both Study ZX008-1501 or ZX008-1504 and Study ZX008-1503.

### **3.5 STUDY MONITORING PROCEDURES**

As in the main Study ZX008-1503, an Independent Data and Safety Monitoring Committee (IDSMC) will be responsible for safety oversight, and a separate International Pediatric Cardiology Advisory Board (IPCAB) will monitor the cardiac safety of the ZX008 clinical trials and provide advice to the IDMSC.

## **4. SELECTION OF STUDY POPULATION**

Patients must fulfill all the entry criteria for Study ZX008-1503 and none of the exclusion criteria, as shown in Sections 4.1 and 4.2, respectively, to qualify for randomization into this sub-study.

### **4.1 INCLUSION CRITERIA**

In addition to meeting all of the main Study ZX008-1503 inclusion criteria subjects in the sub-study must also be willing to wear and use the Embrace watch and parents/caregivers must be willing to use the Alert app. This includes:

1. Subject is willing to wear the Embrace watch on the wrist (alternatively ankle, if needed for younger children). Subjects are asked to wear the watch for as many hours of the day as possible and for the entire night, if possible, for the duration of the sub-study.
2. Subject's parent/caregiver is willing to use the Alert App and receive voice and SMS notifications on their personal smart-phone, and ensure the smart-phone has internet connectivity; iOS 8.2 or higher is required for iPhone users.
3. Subject/subject's caregiver is willing to ensure that the Embrace watch remains within close proximity of the paired iPod Touch running the Empatica Alert app.
4. Subject/subject's caregiver is willing to ensure that the Embrace system is properly stored when not in use, and is not left exposed to direct sunlight, moisture, humidity or rain while in storage. The Embrace watch is water resistant but should never be submerged in water. Bathing and/or showering with the watch is acceptable, however.
5. Subject/subject's caregiver is willing to regularly clean the Embrace watch, routinely inspect the watch for sharp edges and damage, and ensure the watch is never worn over damaged or broken skin.
6. Subject/subject's caregiver is willing to ensure that the Embrace system is properly charged daily during a time when the subject is being observed so any seizures that occur during times that the device is not being worn are able to be added to the record manually.

## **4.2 EXCLUSION CRITERIA**

Subjects meeting any of main Study ZX008-1503 exclusion criteria must not be enrolled into the sub-study. In addition, subject must not be enrolled into the sub-study if:

1. Subject has a known hypersensitivity to any of the Embrace device materials.
2. Subject has a clinically significant condition, or has had clinically relevant symptoms or a clinically significant illness in the 4 weeks prior to Visit 1, other than epilepsy, that would negatively impact study participation, collection of study data, or pose a risk to the subject.

## **4.3 SUBJECTS OF REPRODUCTIVE POTENTIAL**

Female subjects who are sexually active and are of child-bearing potential and male subjects who are sexually active with a partner of child-bearing potential must adhere to the contraception requirements as outlined in the main protocol ZX008-1503.

## **4.4 REMOVAL OF SUBJECTS FROM THERAPY OR ASSESSMENT**

While subjects are encouraged to complete all study evaluations, subjects may voluntarily withdraw from the sub-study for any reason at any time. Subjects who withdraw from the sub-study may still remain in the main study ZX008-1503. These subjects will then use only the ERT seizure diary. Subjects who are withdrawn from the main Study ZX008-1503 (either voluntarily or by the sponsor or investigator) must also be withdrawn from the sub-study. Subjects may be considered withdrawn or withdrawn by the investigator if they fail to return for visits, refuse to follow instructions regarding use of the Embrace watch or associated apps, lose or damage the Embrace in circumstances that do not support replacement, or become lost to follow-up for any other reason. All subjects who withdraw from the study early are required to return the Embrace watch and study iPod.

If premature withdrawal occurs for any reason, the investigator must make a genuine effort to determine the primary reason for a subject's premature withdrawal from the study and record this information on the case report form (CRF). All subjects who withdraw from the study with an ongoing adverse event (AE) must be followed until the event is resolved or deemed stable. If a subject withdraws prematurely after dosing, all data to be collected prior to discharge from the clinical site should be collected at the time of premature discontinuation or at the scheduled discharge.

For subjects who are lost to follow-up (i.e., those subjects whose status is unclear because they failed to appear for study visits without stating an intention to withdraw), the investigator should show "due diligence" by documenting in the source documents the steps taken to contact the subject (eg, dates of telephone calls, registered letters).

Subjects may withdraw their consent to participate in the study at any time without having to justify the reason for doing so. The decision to withdraw consent and discontinue participation in the study will not prejudice the subject's future medical treatment in any way.

In the event that the study is terminated prematurely then the procedure for termination should be followed as described in the main Study ZX008-1503 protocol. Concern for the interests of the subject will always prevail over the interests of the study.

The reason for, and date of discontinuation from participation in the study must be recorded in detail in the CRF and in the subject's medical records (eg, AEs, lack of compliance, lost to follow-up, etc.). If possible, the subject/subject's legal representative should confirm his decision in writing.

The investigator will attempt to complete all procedures usually required at the end of the study at the time when the subject's participation in the study is discontinued or as close as possible to that time, as described in the ZX008-1503 protocol. As far as possible, a complete final examination must be performed on all subjects who do not complete the study according to the study protocol.

Data collected until the time a subject discontinues participation in the study will be handled in the same manner as data for subjects completing the study. Where possible, further information will be collected if any AEs are experienced by a subject after discontinuing participation in the study.

#### **4.5 TERMINATION OF THE SUB-STUDY**

If the investigator, the sponsor, the Medical Monitor, or the IDSMC becomes aware of conditions or events that suggest a possible hazard to subjects if the clinical study or sub-study continues, then the sub-study may be terminated. The sub-study may be terminated at the sponsor's discretion at any time also in the absence of such a finding.

Conditions that may warrant termination of the sub-study include, but are not limited to:

- The discovery of an unexpected, relevant, or unacceptable risk to the subjects enrolled in the clinical study.
- Failure to enroll subjects at the required rate.
- A decision of the sponsor to suspend or discontinue development of ZX008.
- Lack of availability of the Embrace detection device.

#### **4.6 REPLACEMENT OF SUBJECTS**

Enrolled subjects will not be replaced.

## **5. STUDY VISITS AND PROCEDURES**

Subjects participating in the sub-study will undergo all clinic visits and procedures included in the main Study ZX008-1503, plus additional procedures for the sub-study, as described in Table 1. The following questionnaires/scales will be completed at the specified time points:

- To assess user experience with the Embrace watch system, a 5-point Likert Ease of Use Questionnaire ([Appendix 1](#)) will be completed at Clinic Visit 2 (Day 15), monthly at Clinic Visits 3-7, and at the end of study participation (Clinic Visit 8).
- The Perceived Stress Scale (PSS) ([Appendix 2](#)) is the most widely used psychological instrument for measuring the perception of stress. It is a measure of the degree to which situations in one's life are appraised as stressful. It is a 10-item scale that asks about feelings and thoughts during the last month. In each case, respondents are asked how often they felt a certain way. The PSS will be used to evaluate whether objective seizure detection and automated seizure alerts have any impact on perceived stress of the parent/caregiver. This scale will be completed at Clinic Visit 1 (Day 1), monthly at Clinic Visits 3-7, and at the end of study participation (Clinic Visit 8).
- The EQ-5D-5L (see main Study ZX008-1503) is a standardized measure of health status used to provide a simple, generic assessment for clinical and economic appraisal. It consists of 6 questions and can be completed in less than 10 minutes. The EQ-5D-5L is included in the main study ZX008-1503, but for the sub-study the assessment should be as it relates to use of the Embrace watch. This questionnaire will be completed at Clinic Visit 1 (Day 1), monthly at Clinic Visits 3-7, and at the end of study participation (Clinic Visit 8).
- The Hospital Anxiety and Depression Scale (HADS) (see main Study ZX008-1503) is a tool commonly used to determine the levels of anxiety and depression that a person is experiencing. It is a 14-item scale that generates ordinal data. Seven of the items relate to anxiety and 7 relate to depression. The HADS is included in the main study ZX008-1503, but for the sub-study the assessment should be as it relates to use of the Embrace watch. This scale will be completed at Clinic Visit 1 (Day 1) monthly at Clinic Visits 3-7, and at the end of study participation (Clinic Visit 8).

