### **2.2 SECONDARY OBJECTIVES**

The secondary exploratory objectives of the study are:

- To compare objective convulsive seizure count, as captured by the Embrace, to convulsive seizure count captured manually in the electronic seizure diary.
- To compare objective convulsive seizure count during periods of sleep, as captured by the Embrace, to convulsive seizure count during periods of sleep captured manually in the electronic seizure diary.
- To examine if the size of the electrodermal activity (EDA) response during and after a convulsive seizure is reduced over time with ZX008 treatment.
- To examine if skin-surface temperature changes with ZX008 treatment.
- To examine if skin-surface temperature levels are different during periods of time preceding convulsive seizures than during times that are seizure-free.
- To examine correlation of study drug dose and fever-induced convulsive seizure frequency, severity, and duration.
- To examine the timing of diary-reported events vs. automatically detected events.
- To assess quality of life while using the Embrace system with the following measures:
  - Quality of Life (QoL) of the parent/caregiver using the EQ-5D-5L scale.
  - Affective symptoms of the parent/caregiver using the Hospital Anxiety and Depression Scale (HADS).
- To assess caregiver stress using the Perceived Stress Scale (PSS).

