### 3. INVESTIGATIONAL PLAN

#### 3.1 OVERALL STUDY DESIGN AND PLAN

This is a sub-study to the ZX008-1503 OLE study. All participants in this sub-study will have participated in Study ZX008-1501 or ZX008-1504 Cohort 2 in the United States or Canada and then continued in Study ZX008-1503, which is a multicenter, open-label, long-term safety study of ZX008 (fenfluramine hydrochloride) in pediatric and young adult subjects with Dravet syndrome. The main Study ZX008-1503 consists of a 12-month OLE Treatment Period and a 2-week Post-Dosing Period in which all subjects will receive ZX008 starting at 0.2 mg/kg, titrating to an effective dose, up to 0.8 mg/kg/day (not to exceed 30 mg/day). Thus, subjects who complete the main study will have been treated with ZX008 for a minimum of up to 1 year. This sub-study will include up to 20 participants who meet the entry criteria for the main Study ZX008-1503 and who are willing to wear the Embrace watch and their parent/caregiver who is willing to use the Embrace Alert app per the user instructions for 12 consecutive weeks. Those invited to participate will undergo all procedures included in the main Study ZX008-1503, plus any additional procedures for the sub-study. At the conclusion of the sub-study, participants will only use the ERT seizure diary for the remainder of their participation in the main Study ZX008-1503. Efficacy analyses for sub-study participants that rely on the ERT seizure diary or that are specific to the Embrace watch will not be included in the main ZX008-1503 analyses.

At the time of consent for the main Study ZX008-1503 subjects will also be presented with the consent for this sub-study. Subjects who consent to participate in the sub-study will be fitted with an Embrace watch at Study Visit 1. Subjects (and/or parents/caregivers) will also be given instructions on how to use the Embrace system. The Alert app must be running on the provided iPod touch and remain in close proximity of the patient. However, parents/caregivers will continue to use the ERT seizure diary to record the number/type of seizures, use of rescue medication, and study drug administration.

At pre-determined assessment times, parents/caregivers will complete questionnaires specific for the sub-study, including:

1. Ease of Use Questionnaire, which comprises a 5-point Likert scale (1- Very easy, to 5- Very difficult).
2. Perceived Stress Scale (PSS), which consists of 10 items.

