**Table 1: Schedule of Additional Assessments for Subjects Enrolled in the Sub-study**

Study Assessments	Visit 1 a	OLE Treatment Period			
		Visit 2		Visits 3-4 (Months 1-2) b	Visit 5 (EOS/ET) Month 12 c
Study Day	1 a	15		30, 60	90
		Clinic	Phone		
Informed Consent	X				
Entry Criteria	X				
Issue/fit Embrace watch system and provide instructions on its use	X				
Perceived Stress Scale (PSS)	X			X	X
Ease of Use Questionnaire		X		X	X
EQ-5D-5L (QoL of parent/caregiver)	X			X	X
HADS (Affect of parent/caregiver)	X			X	X

Abbreviations: EOS/ET=End of Study/Early Termination; HADS=Hospital Anxiety and Depression Scale; OLE=open-label extension; PSS=Perceived Stress Scale; QoL=Quality of Life

Note: All other Study ZX008-1503 procedures must be completed as described in the main study protocol.

a Visit 1/Day 1 for sub-study ZX008-1503-SS01 corresponds to Visit 1/Day 1 for the main Study ZX008-1503.

b Subjects who continue for an additional 3 months will repeat Study Day 30 and 60 procedures on Study Days 90 and 120, and the end of study visit will be Study Day 150.

c At EOS/ET, subjects will be required to return the Embrace watch and study iPod.

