#### **8.3.2 Efficacy Analysis**

The primary criteria for evaluation in the sub-study is the change over time in the 5-point Likert Ease of Use Questionnaire to measure user experience.

Secondary exploratory efficacy criteria for evaluation include change over time in the following:

- Perceived Stress Scale (PSS) to measure caregiver burden.
- Correlation of monthly (28-day) convulsive seizure count between the Embrace watch and seizure diary.
- Size of EDA response during and in the post-ictal hour of convulsive seizures.
- Skin-surface temperature (measured on wrist).
- Frequency of fever-related convulsive seizures.
- Comparison of convulsive seizure count during periods of sleep, and during the combined titration and maintenance periods between the Embrace watch and seizure diary.
- Correlation of convulsive seizure time and classification as determined by Embrace watch and seizure diary.
- EQ-5D-5L to measure quality of life of the parent/caregiver quality of life while using the Embrace.
- HADS to measure affective symptoms of the parent/caregiver while using the Embrace.

All other efficacy criteria are identical to those in the main Study ZX008-1503.

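### Section 5 says the PSS will show whether seizure detection and alerts affect caregiver stress, but the watch and open-label ZX008 titration share Day 1 with no control group, so the two effects cannot be separated

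*Combined protocol and SAP*

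**What the plan says.** **The question asked.** Protocol Section 5 gives the PSS a causal purpose: "The PSS will be used to evaluate whether objective seizure detection and automated seizure alerts have any impact on perceived stress of the parent/caregiver". For the EQ-5D-5L and the HADS, Section 5 notes that the main study already includes them, then adds "but for the sub-study the assessment should be as it relates to use of the Embrace watch". The objective in Section 2.2 is softer for these two scales ("To assess quality of life while using the Embrace system with the following measures"), as is Section 8.3.2 ("HADS to measure affective symptoms of the parent/caregiver while using the Embrace").

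**The timing.** Section 3.1: "Subjects who consent to participate in the sub-study will be fitted with an Embrace watch at Study Visit 1". Table 1, footnote a: "Visit 1/Day 1 for sub-study ZX008-1503-SS01 corresponds to Visit 1/Day 1 for the main Study ZX008-1503". Section 3.1 describes the main study as one "in which all subjects will receive ZX008 starting at 0.2 mg/kg, titrating to an effective dose". Section 3.3 places the sub-study in the first 12 weeks of that extension, with a possible extension to 24 weeks.

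**The analysis.** Section 8.3.2 lists the PSS, EQ-5D-5L and HADS among secondary exploratory criteria evaluated as change over time. Section 8.4 gives them only general descriptive summaries, with confidence intervals where warranted. It names no comparator, no adjustment for dose or seizure change, and no caveat on attribution.

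**The concern.** The PSS is a general stress scale. Its items (Appendix 2) ask about being upset by the unexpected, feeling unable to control important things, and difficulties piling up. A caregiver's answers can plausibly move with the child's seizures as well as with a watch that sends alerts. Both the watch and the drug titration begin on the baseline day, and the scale looks back one month, so the Day 1 score describes the period before either. Every later score is taken under both.

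The protocol also reads the same weeks in two ways. Section 2.2 treats change in the electrodermal response over this period as something that happens with ZX008; Section 5 treats change in PSS over it as something that happens with alerts.

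At stake is what the sub-study may say about caregivers. A fall in stress could be reported as a benefit of alerts when it came from treatment. Equally, added stress from false alarms could be cancelled by a treatment benefit and missed.

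**Working it through.** **Inputs.** PSS days 1, 30, 60 and 90 (Table 1); up to 20 subjects (Section 3.2); watch start at Visit 1 (Section 3.1); shared Day 1 (Table 1, footnote a); ZX008 given to all (Section 3.1). Section 8.1 rests the sample size on feasibility and gives no effect size, SD, alpha or power, so there is no planned figure to reproduce.

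**Step 1: can the two effects be told apart?** Write the score of caregiver *i* on day *t* as

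Y = a_i + b·W + g·D + error,

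where W is days on the watch and D is days on extension ZX008. Both start on Day 1, so W = D = t − 1, and the model becomes

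Y = a_i + (b + g)(t − 1) + error.

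Only b + g can be estimated. Numerically, 20 subject columns plus 2 exposure columns give 22 columns; the rank is 21. Coding exposure as off on Day 1 and on afterwards gives the same result. Adding subjects or visits changes nothing, because every post-baseline visit is under both. Table 1 schedules no PSS after the watch is returned, when subjects could be on ZX008 alone.

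**Step 2: size of the misattribution.** If the change from Day 1 is read as the watch effect, the error equals the drug-related change, all of it. The documents give no value, so take an assumed range of 1 to 4 PSS points in either direction, on a scale of 0 to 40 (10 items scored 0 to 4).
- Watch effect 0, drug-related change −4 to −1: reported change −4 to −1, read as relief from alerts.
- Watch effect 0, drug-related change +1 to +4: reported change +1 to +4, read as a burden from alerts.
- Watch effect +2, drug-related change −2: reported change 0, and the added stress disappears.

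Precision does not help. With 20 caregivers the 95% half-width for mean change is 2.093/√20 = 0.47 SD of change, but that interval is around b + g.

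**Step 3: do the HADS and EQ-5D-5L escape through their instruction?** No. Section 5 describes them as measures of anxiety and depression and of general health status. Asking respondents to answer in relation to the watch does not remove the drug's contribution. On Day 1 the watch is only being fitted, so there is no use to relate the answer to, and the baseline and later scores answer different questions.

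**Step 4: what would a concurrent group without a watch give?** Section 5 says: "The HADS is included in the main study ZX008-1503", and the same of the EQ-5D-5L. With 20 watch users and m comparators on the same extension schedule (m is assumed), the half-width for the difference in change is 1.96·√(1/20 + 1/m):
- m = 20: 0.62 SD
- m = 40: 0.54 SD
- m = 100: 0.48 SD

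Power for a difference of 0.5 SD would be about 35%, 45% and 53%. The watch effect becomes estimable, subject to selection, but imprecisely. The PSS is described in Section 3.1 as specific to the sub-study, so no such group can be assumed for it.

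**The case against.** The strongest reply is about scope. These are secondary exploratory measures in a pilot of up to 20; the primary criterion, Ease of Use, is untouched; and Section 8.4 defers full methods to an SAP finalised before database lock. That limits the consequence. It does not make the Section 5 question answerable, because no later analysis choice can separate exposures that coincide.

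One could also say that dose and wear time will vary between subjects, which breaks exact collinearity. It does, but Section 3.1 has dose titrated to effect and wear time is chosen by the family, so neither gives a clean contrast, and neither is planned.

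Four stronger readings are tempting, and the documents do not support them:
- **That all three scales are formally read as watch effects.** Only the PSS sentence speaks of impact. The HADS and EQ-5D-5L wording is softer, although the instruction leans toward the device.
- **That a benefit from fewer seizures will be credited to the watch.** Section 1.1 and Appendix 3 show that entrants come from core-study treatment, which for ZX008-1504 Cohort 2 was with ZX008. Day 1 need not be first exposure, and nothing states which way seizure control will move.
- **That a spurious significant watch effect will appear in some given share of trials.** Section 8.4 plans no test on these scales, and there is no effect size or SD from which to calculate such a rate.
- **That a ready comparator exists.** The main-study visit schedule is not in these documents, and Section 5 alters the instruction for sub-study caregivers, so scores would not be like for like.

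Finally, no sentence dates the first extension dose; the same-day start is inferred from the shared Day 1 and the initial 12-week window.

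**Conclusion.** The concern holds for the PSS. The stated purpose, to evaluate the impact of detection and alerts, cannot be met by single-arm change from a Day 1 shared with open-label titration. The error equals the whole drug-related change. Its direction is unknown and its size cannot be derived from the documents; the 1 to 4 points used above is an assumption. The HADS and EQ-5D-5L share the problem in milder form through the watch-related instruction. The conclusion rests on one inference, that extension dosing starts at the shared Visit 1. It is worth correcting because it limits what may be concluded about caregivers, but it does not affect the primary usability assessment.

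**What to change.** 1. In Section 5, replace the PSS sentence with one stating that the scale is used *to describe caregiver stress during combined use of the watch and open-label ZX008*. State in Section 8.4 that no change in PSS, HADS or EQ-5D-5L will be attributed to the watch alone.
2. Report each caregiver's PSS change beside the subject's change in ERT-diary convulsive seizures, naming the reference period. Label this as descriptive context only. Alerts reach the caregiver who keeps the diary, and Section 1.2 expects the technology to help with unwitnessed sleep seizures, so the watch may itself alter diary counts. This does not separate drug from device.
3. For the HADS and EQ-5D-5L, use the standard main-study instruction. Where main-study visits coincide (to be confirmed against that protocol), show sub-study change beside change in concurrent ZX008-1503 caregivers without a watch, adjusted for the Day 1 score.

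**Cost.** Protocol and SAP wording and two small tables. Seizure diary data are already collected, and Section 5 says the main study includes the HADS and EQ-5D-5L. No change to treatment, visits or sample size. The drawback is that the comparison in item 3 is not randomised, families who volunteer for a watch may differ, and with up to 20 watch users it is imprecise (0.48 to 0.62 SD under the assumed group sizes), so it stays descriptive. Item 1 stands even if item 3 proves unworkable.

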3. Parents/caregivers will also complete the EQ-5D-5L and HADS in order to assess quality of life while using the Embrace.

A schedule of sub-study assessments is provided in Table 1.

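### EQ-5D-5L and HADS are to be answered in relation to the watch from Day 1, when the watch is only being issued, so change from Day 1 is not interpretable as written

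*Combined protocol and SAP*

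**What the plan says.** Section 5 (Study Visits and Procedures) describes the EQ-5D-5L as a standardized, generic measure of health status and the HADS as a measure of a person's level of anxiety and depression. It notes that both belong to the main study, and then adds for each that "for the sub-study the assessment should be as it relates to use of the Embrace watch".

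On timing, Section 5 says of the EQ-5D-5L: "This questionnaire will be completed at Clinic Visit 1 (Day 1), monthly at Clinic Visits 3-7", with a last completion at the end of participation. The HADS has the same schedule, and Table 1 marks both scales at Visit 1. Section 3.1 says that consenting subjects "will be fitted with an Embrace watch at Study Visit 1". Table 1, footnote a, adds that "Visit 1/Day 1 for sub-study ZX008-1503-SS01 corresponds to Visit 1/Day 1 for the main Study ZX008-1503".

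On use, Section 3.1 states: "Parents/caregivers will also complete the EQ-5D-5L and HADS in order to assess quality of life while using the Embrace". Section 8.3.2 says "Secondary exploratory efficacy criteria for evaluation include change over time in the following", and the list that follows includes both scales, the second as "HADS to measure affective symptoms of the parent/caregiver while using the Embrace". Section 8.4 gives no scoring or analysis rule for a watch-related version of either scale.

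**The concern.** A general scale measures a device's impact by being asked the same way before and during use. Here the caregiver is told to relate health status, anxiety and depression to a device first received at that visit. Either the Day 1 answers relate to nothing, or caregivers answer Day 1 in general terms and later visits in watch-related terms. In both cases the difference from Day 1 is not a clean measure of change in the caregiver. At stake is the only pre-use reference value for two of the caregiver outcomes in the secondary objectives.

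**Working it through.** The plan states no effect size, SD or power for these scales, and Section 8.1 bases the sample size on feasibility, so there is no planned figure to reproduce. The check compares sections and counts administrations.

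1. **What Day 1 can measure.** The clause in Section 5 covers both scales and every visit. Section 3.1 and Table 1 place issue and fitting of the watch at Visit 1. The order within that visit is not stated, but in either order there has been no period of sub-study use to report on.

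2. **What change from Day 1 contains.** Let G(t) be the score a caregiver would give on the standard form at visit t, and W(t) the score under the watch-related framing.
   - Day 1 answered generally, later visits watch-related: W(t) − G(1) = [G(t) − G(1)] + [W(t) − G(t)]. The first bracket is real change; the second is the shift caused by the framing. The documents give nothing from which to estimate the second.
   - Clause followed on Day 1 as well: W(1) has no defined meaning, so neither has W(t) − W(1).
   - Two post-baseline visits s and t: W(t) − W(s) uses one framing and can be described, but the properties of W are unknown.
   - Standard form throughout: G(t) − G(1), with Day 1 as an ordinary pre-use baseline.

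3. **Comparison with the other two questionnaires.** The Ease of Use Questionnaire does ask about the watch, and Table 1 starts it at Visit 2 (Day 15), not Day 1. The PSS is intended to show whether detection and alerts affect caregiver stress. It carries no watch framing and does have a Day 1 value: "This scale will be completed at Clinic Visit 1 (Day 1), monthly at Clinic Visits 3-7". The EQ-5D-5L and HADS combine the framing of the first with the schedule of the second.

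4. **Whether the reframing can be carried out.** No watch-related version is supplied. Appendices 1 and 2 contain only the Ease of Use Questionnaire and the PSS; for the other two the reader is sent to the main study. Staff at the 5 to 10 sites in Section 3.4 would have to find their own wording.

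5. **How many administrations are compared with Day 1.**
   - Table 1: Days 1, 30, 60, 90 = 4, of which 4 − 1 = 3 are post-baseline.
   - Table 1 with footnote b: Days 1, 30, 60, 90, 120, 150 = 6, of which 6 − 1 = 5.
   - Section 5: Visit 1, Visits 3 to 7, Visit 8 = 1 + 5 + 1 = 7, of which 7 − 1 = 6.

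   The last count conflicts with Table 1, and the two need reconciling in any case.

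6. **Share of the criteria.** Section 8.3.2 lists nine secondary exploratory criteria; two are affected. The primary criterion and the PSS are not.

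**The case against.** The clause may not be meant as an instruction to caregivers at all. The objectives, Section 3.1 and Section 8.3.2 describe outcomes over a period of watch use, no modified form exists, and Section 5 points to the main-study forms. On that reading Day 1 is an ordinary baseline. This is possible, but the clause is worded as a contrast with the main study and as a statement of what the assessment should be. If it changes nothing it has no function, and sites are left to guess. The SAP to which Section 8.4 defers cannot settle how forms are administered.

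Section 8.3.2 also says change over time, not change from Day 1. That stands in part. A reader might infer that all change on these scales is meaningless; the documents do not support that, because later visits would share one framing.

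A reader might further infer that main-study EQ-5D-5L and HADS data are altered, since Visit 1 is shared. This is neither confirmed nor excluded. The main protocol is not available, and the text does not say whether one completion serves both studies. Sections 3.1 and 8.4 keep Embrace-specific efficacy analyses out of the main analyses, without saying how these two scales are handled. If caregivers do answer Day 1 in general terms, nothing reframed enters at that visit. Nor is any comparison planned with main-study caregivers outside the sub-study, so loss of such comparability is not a defect of this plan.

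Finally, removing the clause gives up an apparent wish for device-related information, and standard scores would not isolate the watch. Both points are true and are carried into the fix as limits.

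**Conclusion.** The point holds in a limited form. As written, the Day 1 EQ-5D-5L and HADS scores have no clear referent, and change from Day 1 is not interpretable for these two secondary exploratory criteria. Description across post-baseline visits survives, with unknown validity. The size of any framing shift cannot be estimated from the documents.

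The conclusion assumes that the clause governs how the forms are answered. If it guides interpretation only, the defect reduces to ambiguous wording, which the same edit removes. Effects on main-study data remain a possibility to be clarified, not a finding. With up to 20 subjects and an unaffected primary criterion, severity is low to moderate.

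**What to change.** - In Section 5, delete the clause tying the assessment to the watch, once for the EQ-5D-5L and once for the HADS.
- State that the standard, unmodified forms are administered and scored at every visit, and that the Day 1 forms are completed before the watch is fitted.
- In Section 8.4, describe within-caregiver change from Day 1 as quality of life and affect during the period of watch use, in line with the approach to the PSS. This still meets the stated objective.
- State whether main-study and sub-study completions are the same or separate. Which is workable depends on the main-study schedule.
- Reconcile the visit list in Section 5 with Table 1.

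The cost is two deleted clauses, a few added sentences and one retraining point for sites; no new data are needed. The downside is that the scores no longer purport to be watch-specific. With no control group, and the open-label period starting at the same visit as watch use, change from Day 1 cannot be attributed to the watch, and the report should say so.
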